## 7.5 Stopping Rules

This study does not contain any stopping rules as it does not include treatment for patients.

**8.0 DRUG/TREATMENT INFORMATION**

Not applicable.

**9.0 CORRELATIVES/SPECIAL STUDIES**

Standard clinical history including clinical histopathology will be collected and correlated. No additional correlative studies are collected.

**10.0 STATISTICAL CONSIDERATIONS**

**10.1 Study Design/Study Endpoints**

This is a prospective, single-centered study, designed to address the following primary objective:

1. To determine whether ASL-measured perfusion can identify treatment response (time to progression) earlier than the currently used RECIST criteria (tumor size).  
*Hypothesis: Greater reduction in ASL measured tumor perfusion during and immediately after treatment is a marker of tumor responsiveness prior to size changes.*

Primary end points for this study will include the absolute days of time to disease progression, PFS and OS as well as disease status (progression versus not) at 7 months post treatment initiation. Progression will be determined based on clinically accepted RECIST criteria (20).

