### **2.0 STUDY OBJECTIVES**

#### **2.1 Primary Objectives**

- 2.1.1 To determine whether ASL-measured perfusion can identify treatment response (time to progression) earlier than the currently used RECIST criteria in patients undergoing anti-angiogenic treatment.

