#### **2.2 Secondary Objectives**

- 2.2.1 To determine the correlation between ASL-measured baseline perfusion and the treatment response (PFS, OS).
- 2.2.2 To determine the correlation between post-treatment changes in ASL-measured perfusion at T1, T2 and T3 compared to baseline and the treatment response (PFS, OS).
- 2.2.3. To predict responders from non-responders (progression versus not at 7 months) with measurements at baseline and at earlier time points (T1 and T2) using:
  - a. ASL-measured perfusion alone
  - b. ASL-measured perfusion in combination with other MR imaging metrics such as diffusion weighted imaging (DWI) derived apparent diffusion coefficient (ADC), and chemical exchange saturation transfer (CEST) measured CEST effect.

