#### **2.4 Endpoints**

Primary end points for this study will include the absolute days of progression free survival (PFS) and overall survival (OS). Additionally disease status (progression versus not) at 7 months and survival (dead or alive) at 24 months post-treatment initiation will also be documented. Progression will be determined based on the clinically accepted RECIST criteria.

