#### 6.1.5 Progression-Free Survival

Progression-free survival (PFS) is defined as the duration of time from start of treatment to time of progression.

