**10.2 Sample Size and Accrual**

The sample size is calculated based on the primary objective. A significant correlation of 0.75 was observed between one month ASL perfusion change and time to progression in our RCC patients, whereas the corresponding tumor size change was not correlated with time to progression (19). We expect approximately 50% of RCC patients to progress within 7 months of imaging protocol. Beyond this time point, patients will be followed according to their clinical scans for the next 3 years or until death. Using such information, we target 40 subjects for this study and anticipate approximately 20 subjects to progress within the 7 months period. This sample size would provide more than 95% power to detect a correlation of 0.75 between earlier perfusion changes (at T2 and T6) and time to progression, using two-sided correlation test at a significance level of 0.05.

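### The lists of primary endpoints disagree, and one unadjusted 0.05 covers two time points with no deciding rule, so 0.05 is not guaranteed for the primary claim

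*Combined protocol and SAP*

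**What the plan says.** The documents describe the primary endpoint in several places that do not agree.

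- **Section 10.1**, matched by the Study Summary, lists four: "Primary end points for this study will include the absolute days of time to disease progression, PFS and OS as well as disease status" at 7 months.
- **Section 2.4** lists two: "Primary end points for this study will include the absolute days of progression free survival (PFS) and overall survival (OS". It does not mention time to progression. It then gives 7-month status a lesser standing and adds an item absent from 10.1: "Additionally disease status (progression versus not) at 7 months and survival (dead or alive) at 24 months post-treatment initiation will also be documented".
- **Section 2.1.1**, the only primary objective, rests on time to progression: "To determine whether ASL-measured perfusion can identify treatment response (time to progression) earlier than the currently used RECIST criteria in patients undergoing anti-angiogenic treatment". Section 10.1 restates this objective without the limit to anti-angiogenic treatment.
- **Section 2.2** uses PFS and OS for secondary objectives, for example "To determine the correlation between ASL-measured baseline perfusion and the treatment response (PFS, OS" in 2.2.1. Objective 2.2.3 does the same with 7-month status.
- **Section 6.1.5** defines PFS without naming death: "Progression-free survival (PFS) is defined as the duration of time from start of treatment to time of progression".

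The only significance level is in section 10.2, for the correlation of perfusion change at T2 and T6 with time to progression, "using two-sided correlation test at a significance level of 0.05". The time and events table for RCC subjects (5.4) runs from T0 to T5. Section 10.3 refers to perfusion change during and immediately after treatment, which identifies no single visit. No section gives a multiplicity adjustment, a testing order, a deciding time point, or a rule on whether one or both time points must succeed.

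**The concern.** A reader of the final report should be able to tell which result was meant to answer the primary objective. Under this plan several results could be presented in that role: a correlation with time to progression at either of two visits or, going by the labels in 2.4 and 10.1, a result for PFS, OS or 7-month status. If the choice can be made after the data are seen, the stated 0.05 no longer describes the chance of a false positive primary claim. With about 20 progressors expected, a prespecified result and a selected one could not be told apart.

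**Working it through.** **Inputs.** From 10.2: correlation 0.75, 40 subjects, about 20 progressors, two-sided 0.05, two time points. From 10.3: the correlation test uses patients with progression, so n is about 20. The correlation between perfusion changes at the two visits is not given. I assume 0.5, 0.7 and 0.9, with independence as the reference.

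**1. The plan's own power figure.** Section 10.2 says "This sample size would provide more than 95% power to detect a correlation of 0.75". By Fisher's z, power = Φ(atanh(r)·√(n−3) − z).
- atanh(0.75) = 0.973 and √17 = 4.123, with product 4.012.
- 4.012 − 1.960 = 2.052, so power is 98.0% (98.4% by simulating the t-test of Pearson's r).

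The stated figure is reproduced at n = 20.

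**2. False-positive rate over the two time points in 10.2, each at 0.05.**

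| Rule | Assumption | Rate |
|---|---|---|
| Either suffices | independent: 1 − 0.95² | 9.75% |
| Either suffices | correlation 0.5 | 9.2% |
| Either suffices | correlation 0.7 | 8.4% |
| Either suffices | correlation 0.9 | 7.1% |
| Either suffices | upper bound: 2 × 0.05 | 10% |
| Both required | any | at most 5% |

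The correlated rows come from 200,000 simulated data sets of 20 patients, with two correlated perfusion changes tested against one unrelated outcome.

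**3. How many distinct endpoints are listed.** Under 6.1.5, PFS runs from start of treatment to progression, so as written it equals time to progression. Section 10.3 forms responders and non-responders by cutting PFS at 7 months, so 7-month status is a dichotomy of the same variable. The four names in 10.1 cover at most three distinct endpoints: time to progression, its 7-month dichotomy, and OS.

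**4. Power if alpha is split over two time points.** At 0.025 each, z = 2.241 and 4.012 − 2.241 = 1.770, so power is 96.2% (96.8% simulated). The progressors needed for 95% power are ((z + 1.645)/0.973)² + 3, rounded up: 17 at 0.05 and 19 at 0.025. The stated power survives the split with 20 progressors.

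**The case against.** The plan goes some way towards identifying the deciding analysis. Section 10.1 sets out one primary objective, 10.2 sizes the study on it, and 10.3 tests it by correlation. The Cox and logistic models in 10.3 match secondary objectives 2.2.1 to 2.2.3. Read this way, much of the conflict is labelling, and what remains is two time points. The wording in 10.2 could also mean that both must succeed, in which case the error stays within 5%. This objection stands to the extent that inflation is possible, not demonstrated. It does not remove the contradiction between 2.4 and 10.1, and it supplies no written rule.

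A reader might go further, multiply four endpoints by two time points, and quote 1 − 0.95⁸ = 33.7%. The documents do not support that figure. Only the correlation with time to progression carries a stated 0.05, and the Cox and logistic models have no stated level. The four endpoints are not four separate quantities, and independence is untenable when one is a dichotomy of another. One of the two time points is not in the schedule, so even the number of primary tests is unsettled.

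**Conclusion.** The point holds as an inconsistency in the endpoint hierarchy with a modest, conditional effect on the error rate. The sections disagree on which endpoint is primary, and 2.4 omits the one that the objective and sample size use. The 0.05 in 10.2 is not guaranteed for the primary claim. If success at either of two time points is enough, the rate is about 7 to 10%, given the assumed correlations of 0.5 to 0.9 up to independence. If both are required, it is at most 5%. If any other listed endpoint could also support the claim, the rate would be higher, but the plan does not define that family well enough to give a firm number. A reader might infer that the true error is already far above 0.05. The documents show only that nothing holds it at 0.05. This should be corrected, but it does not invalidate the study.

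**What to change.** 1. In the Study Summary, 2.4, 10.1 and 10.2, name time to progression, in the population of objective 2.1.1, as the sole primary endpoint.
2. Reconcile T6 in 10.2 with the T0 to T5 schedule.
3. Then choose one of two routes.
   - Prespecify and justify one deciding time point at two-sided 0.05. T2 is the only visit named in 10.2 that exists in the schedule, but the supporting 0.75 came from one-month change while T2 is day 14, so the plan does not dictate this choice.
   - Test two time points at 0.025 each, with success at either sufficient.
4. List PFS, OS, 7-month status and all other time points as secondary, reported with confidence intervals and no confirmatory claim.

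The cost is wording in four places, and fewer results can be called primary. No extra patients are needed if about 20 progressors fall within the 2.1.1 population. Because 3.1.2 also admits patients on immunotherapy, the team should confirm that count against the 17 (at 0.05) or 19 (at 0.025) needed for 95% power.

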**10.2 Sample Size and Accrual**

The sample size is calculated based on the primary objective. A significant correlation of 0.75 was observed between one month ASL perfusion change and time to progression in our RCC patients, whereas the corresponding tumor size change was not correlated with time to progression (19). We expect approximately 50% of RCC patients to progress within 7 months of imaging protocol. Beyond this time point, patients will be followed according to their clinical scans for the next 3 years or until death. Using such information, we target 40 subjects for this study and anticipate approximately 20 subjects to progress within the 7 months period. This sample size would provide more than 95% power to detect a correlation of 0.75 between earlier perfusion changes (at T2 and T6) and time to progression, using two-sided correlation test at a significance level of 0.05.

**10.3 Data Analyses Plans**

The perfusion difference images and the absolute quantified images will be converted to DICOM and transferred to a DICOM database (e.g. iPACS, OsiriX). A semi-automated segmentation algorithm and region of interest (ROI) based measures will be performed to extract perfusion measures. Percentage changes in perfusion within each ROI will be calculated at each follow-up MRI compared to the baseline image. The semi-automated tumor ROIs will be compared to expert segmentation by [name] in all cases, who will also supervise the trainee (to be recruited) in the analysis. Additionally, morphological changes will also be calculated according to RECIST and 10% reduction in the sum of the largest diameters (20).

Among patients with disease progression, one-sample correlation test will be used to determine the correlation between change in ASL measured tumor perfusion during and immediately after treatment and time to progression, and the correlation between change in ASL measured tumor perfusion during and immediately after treatment and the corresponding tumor size change. The correlations will be measured and compared using Pearson's correlation coefficient along with 95% confidence interval. PFS and OS will be correlated with baseline perfusion and post-treatment changes at T1 and T2

compared to baseline using univariable and multivariable Cox regression models. We used PFS at 7 months as a cutoff point to divide patients into “responders” versus “non-responders” in this study. Univariable and multivariable logistic regression models will be used to predict responders from non-responders with ASL measurements at baseline and at earlier time points (T1 and T2) alone, and in combination with other MR imaging metrics. The statistical analysis will also be performed separately for male and female subjects to evaluate sex as a biological variable.

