## STUDY SUMMARY

Title	A Prospective Study to Evaluate Quantitative Non-Contrast Perfusion using Arterial Spin Labeled MR Imaging for Assessment of Therapy Response in Metastatic Renal Cell Carcinoma
Short Title	Quantitative MRI for therapy response assessment in metastatic RCC
Protocol Number	STU 032018-078
Phase	N/A
Methodology	Prospective study to evaluate quantitative MRI metrics for the assessment of treatment response
Study Duration	48 months
Study Center(s)	Single-center
Objectives	To prospectively determine whether ASL-measured perfusion can identify treatment response earlier than the currently used RECIST criteria.
Number of Subjects	90 (40 subjects with RCC and 50 healthy volunteers)
Diagnosis and Main Inclusion Criteria	Diagnosis: Locally advanced or metastatic renal cell carcinoma Main Inclusion Criteria: Patients with histologically proven clear cell RCC, scheduled to undergo anti-angiogenic treatment or immunotherapy (IO) who are 18 years of age and older and have no contraindication to MRI.
Study Product(s), Dose, Route, Regimen	N/A
Duration of administration	N/A
Reference therapy	N/A
Statistical Methodology	Primary end points for this study will include the absolute days of time to disease progression, progression free survival (PFS) and overall survival (OS) as well as disease status (progression versus not) at 7 months post treatment initiation. Progression will be determined according to the clinical RECIST criteria. One-sample correlation test will be used to determine the correlation between change in ASL measured tumor perfusion during and immediately after treatment and time to progression, and the correlation between change in ASL measured tumor perfusion and the corresponding tumor size change. The correlations will be measured and compared using Pearson's correlation coefficient along with 95% confidence interval. PFS and OS will be correlated with baseline perfusion and post-treatment changes at T1, T2 and T3 compared to baseline using univariable and multivariable Cox regression models. Univariable and multivariable logistic regression models will be used to predict responders from non-responders (progression versus not at 7 months) with ASL measurements at baseline and at earlier time points (T1 and T2) alone, and in combination with other MR imaging metrics.

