#### 5.4 Time and Events Table

##### RCC Subjects

	Pre-study	Week 0 (T0) before initiation of anti-angiogenic therapy	Day 7±2 (T1)	Day 14±2 (T2)	T3	T4	T5	Follow-up (As indicated by clinical protocol)
Assessment	X							
Informed Consent	X							
History and PE	X							
Tumor Measurements	X							
MRI*		X	X	X	X	X	X	X

\*Clinically, metastatic RCC patients are imaged every 2-3 months after the initiation of anti-angiogenic therapy, since morphological (i.e. size) changes are not anticipated earlier. However, our preliminary experience has shown functional changes including perfusion as early as 2-weeks after the initiation of the treatment (19). T0, T1, and T2 sessions will be performed for this proposal, while T3, T4, and T5 will be performed along with the clinical imaging sessions. The research MR imaging may take approximately an additional 15 minutes per each imaging session, when done in conjunction with the clinical imaging. The T0, T1, and T2 research MR imaging sessions will be performed additionally for the purpose of this study, with each taking approximately one hour.

The ASL portion of the study does not require contrast. Clinically, the subjects will also receive gadolinium based contrast injection for the MRI study to measure the blood flow to the tumors. This is done at the clinical imaging time points of T3, T4, and T5. Similar to this, the contrast agent will also be administered during the research portion of the study at T0, T1 and T2 time points, to compare the blood flow measured with ASL-MRI.

MRI including ASL will be performed before, during and after the treatment, in a total of 6 MRI sessions until 7 months after the first session, or when progression is clinically indicated. Thereafter, patients will be followed through standard clinical examinations for the next 3 years or until demise, whichever occurs first.

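### The correlation that sizes the study is run only in patients who progress, so the rest are dropped on their outcome; a Cox model for time to progression should lead, with a stated data cut-off and a tumor-size analysis

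*Combined protocol and SAP*

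**What the plan says.** **The test.** Section 10.3 relates perfusion change to time to progression in a restricted set: "Among patients with disease progression, one-sample correlation test will be used to determine the correlation between change in ASL measured tumor perfusion". The Statistical Methodology entry of the Study Summary gives the same test with no restriction: "One-sample correlation test will be used to determine the correlation between change in ASL measured tumor perfusion".

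**The sizing.** Section 10.2 takes its effect size from prior data: "A significant correlation of 0.75 was observed between one month ASL perfusion change and time to progression in our RCC patients". It plans 40 RCC patients, expects about 20 to progress by 7 months, and claims more than 95% power (two-sided 0.05) for a correlation of 0.75 "between earlier perfusion changes (at T2 and T6) and time to progression". It adds: "Beyond this time point, patients will be followed according to their clinical scans for the next 3 years or until death". It gives no data cut-off for the analysis.

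**The scan.** The schedule in section 5.4 runs from T0 to T5, so there is no T6. T1 is day 7±2 and T2 is day 14±2. T3 to T5 accompany clinical imaging, and "metastatic RCC patients are imaged every 2-3 months after the initiation of anti-angiogenic therapy". No RCC scan is scheduled at one month.

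**The Cox models.** Section 10.3 also plans Cox models for PFS and OS on baseline perfusion and the T1 and T2 changes; the Study Summary adds T3. These serve secondary objectives 2.2.1 and 2.2.2 and are not sized.

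**The endpoints.** Section 6.1.5 reads: "Progression-free survival (PFS) is defined as the duration of time from start of treatment to time of progression". Death is not mentioned, so PFS as defined is the same as time to progression, yet section 10.1 lists the two separately: "Primary end points for this study will include the absolute days of time to disease progression, PFS and OS".

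**The comparator and population.** The primary objective compares ASL with RECIST size criteria. Section 10.3 correlates perfusion change with time to progression and with size change, but never size change with time to progression. Objective 2.1.1 covers anti-angiogenic treatment only, while criterion 3.1.2 also admits immunotherapy patients, and no split of the 40 is given.

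**The concern.** Whether a patient enters the main test depends on the outcome being predicted. The patients left out are those who have gone longest without progressing, and these are the patients in whom a useful perfusion marker should look most different. Removing them narrows the range of time to progression, which pulls the correlation towards zero, and it discards the information in their progression-free time. Following the Study Summary instead does not help, because a patient with no progression date has no value to correlate.

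What is at stake is a missed association, not a false one. In addition, even a strong perfusion correlation would not answer the primary question, because nothing shows how size change performs against the same outcome.

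**Working it through.** **1. The plan's own figure.** Inputs from section 10.2: r = 0.75, about 20 progressors, two-sided alpha 0.05. Fisher z power is Φ(atanh(r)·√(n−3) − 1.96).
- n = 20: 0.973 × √17 = 4.012; 4.012 − 1.960 = 2.052; power 98.0%. The claim of more than 95% is reproduced.
- It stays above 95% down to 17 progressors (95.4%).
- The calculation takes 0.75 to be the correlation within progressors.

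**2. Effect of keeping only the earlier half.** Suppose instead that rho describes all patients (bivariate normal) and only those below the median time are kept. The variance of the kept half is s² = 1 − 2/π = 0.363 of the whole, and the correlation becomes rho·s / √(1 − rho² + rho²s²).
- rho 0.75: 0.452 / 0.801 = 0.56; power at n = 20 is 75%.
- rho 0.5: 0.301 / 0.917 = 0.33; power 29%.
- To see 0.75 among progressors, the all-patient value would have to be about 0.88.

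**3. Progressor-only Pearson against Cox, by simulation.** Assumptions:
- 40 patients, with exponential times and a 7-month median, from the 50% progressing by 7 months in section 10.2.
- An all-patient rho linking perfusion change to time to progression.
- Cox fitted to all patients; 2,000 to 4,000 trials per setting.
- The 7-48 month spread is assumed from the 48-month study duration in the Study Summary.
- Ranges cover Pearson on raw days or on a log-type scale, and repeated runs.

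| Follow-up | Progressors of 40 | rho 0.75, Pearson v Cox | rho 0.5, Pearson v Cox |
|---|---|---|---|
| 7 months | about 20 | 69-78% v 99.8-99.9% | 26-31% v 82-84% |
| Spread over 7-48 months | about 35 | 99.6-99.8% v 100% | 72-81% v 87-89% |
| 36-43 months for all | about 39 | 99.9-100% v 100% | 82-91% v 87-89% |

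With no association, the progressor-only test rejects in about 5% of trials (4.6-5.2%).

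**4. What these Cox figures leave out.** They have no delayed entry at the scan and treat progression dates as exact. With entry at day 14 and assessment every 2.5 months (43 months, rho 0.5), Cox power is 82% and Pearson 77-81%.

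**5. A smaller anti-angiogenic subset.** The size is not given; 20 is assumed, with rho 0.5.
- 43 months for all: Pearson 54-62% v Cox 61%.
- 7-48 months: Pearson 43-49% v Cox 59-60%.

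Both methods lose power. The gap follows the length of follow-up, not the subset size.

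**6. Deaths without progression.** Assumed 9% or 18% of patients, unrelated to perfusion; rho 0.5, 7-48 months.
- Cox with deaths censored: 86% or 84%.
- Cox with deaths as events: 82% or 75%.
- Pearson: 68% or 61%.

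The rule matters enough to state.

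**7. Sizing a Cox lead analysis.** The detectable hazard ratio per SD is exp((1.96 + z) / √events), where z is the normal quantile for the power. With 20 events: exp(2.80 / 4.47) = 1.87 at 80% power and 2.06 at 90%. With 30 events: 1.67 and 1.81.

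**The case against.** The strongest reply is that follow-up is long. Section 10.2 follows patients for 3 years beyond the 7-month imaging period, about 43 months each. By then nearly all would have progressed, few are dropped, and neither method clearly wins. This stands as far as it goes. But the only progressor count in section 10.2 is the 7-month one, and section 10.3 names no cut-off. If the 48-month duration is also the analysis horizon, 43 months each leaves 48 − 43 = 5 months to enrol all 40. Sections 4.6 and 5.3 place the 3 years after the study's conclusion, so the documents do not settle which applies.

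Second, section 10.2 pairs 0.75 with about 20 progressors and section 10.3 tests progressors, so on the plan's own reading power is 98%. That also stands. The documents do not say which patients the prior 0.75 describes, so a reader might infer that the power statement is wrong or the study underpowered; the documents do not support that. Nor do they support reading the restriction as a source of false positives.

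Third, Cox models are already planned. They are, but for PFS and OS, at several scans and for secondary objectives. The model proposed here adapts them and is not the same analysis.

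Two further inferences fail. A small anti-angiogenic subset does not by itself create the gap between methods. A size model at an early scan does not test superiority to RECIST: section 5.4 does not expect size change before the first clinical imaging, and two hazard ratios side by side are not a formal comparison.

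**Conclusion.** The point holds as a cheap improvement. The main test selects patients on the outcome, the Study Summary and section 10.3 disagree on who is analysed, and the primary comparison with tumor size has no analysis behind it. The power arithmetic is sound and type I error is kept for a single test.

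The loss ranges from large (more than 50 percentage points at rho 0.5 with a 7-month cut), through roughly 6 to 17 points with follow-up spread over 7-48 months, to no clear difference at 36-43 months each. These figures rest on 40 patients, exponential times with a 7-month median and an all-patient correlation. The Cox values should be read a few points lower once delayed entry and 2-3-monthly assessment are included. Confidence in the size is moderate because the cut-off is unknown.

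**What to change.** 1. Make a Cox model for time to RECIST progression the lead analysis, adapting the models in section 10.3. Use perfusion change from baseline to one named scan, in all anti-angiogenic patients with both scans. Patients enter the risk set at that scan, and those without progression are censored at last assessment.
2. Keep the progressor-only Pearson correlation as descriptive.
3. Fit the same model for tumor-size change at the same scan. Report both hazard ratios per SD with 95% confidence intervals, as supporting evidence on whether perfusion changes come before size changes, not as a test of superiority to RECIST.
4. In section 10.2, state the data cut-off, which patients 0.75 describes, the number of anti-angiogenic patients and the power of the lead model. Reconcile the scans named there with the T0-T5 schedule and with the one-month source of 0.75.
5. Make the Study Summary and section 10.3 state the same analysis set.
6. Amend section 6.1.5 so that PFS and time to progression differ in how deaths without progression count; for example, censored for time to progression and counted as events for PFS.

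**Cost.** A protocol amendment with IRB approval (section 11.6), with no added scans or follow-up. A hazard ratio is less directly comparable with the prior 0.75. The Cox likelihood-ratio test is slightly liberal at about 20 patients (5.4-6.3% in simulation). The Study Schema makes attending both T1 and T2 optional, so some patients may lack the named scan, and they would be lost to either method.

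### The perfusion-change versus size-change correlation is limited to progressors although it needs no progression date, which discards usable patients and selects on a partly size-based outcome

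*Combined protocol and SAP*

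**What the plan says.** Section 10.3 defines the analysis set at the start of one sentence: "Among patients with disease progression, one-sample correlation test will be used to determine the correlation between change in ASL measured tumor perfusion". The first correlation under that clause is with time to progression. The sentence then continues: "and the correlation between change in ASL measured tumor perfusion during and immediately after treatment and the corresponding tumor size change". Read naturally, the opening clause governs both. No reason is given for limiting the second.

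The two variables in the second correlation are described earlier in 10.3 with no condition on progression. For perfusion: "Percentage changes in perfusion within each ROI will be calculated at each follow-up MRI compared to the baseline image". For size: "morphological changes will also be calculated according to RECIST and 10% reduction in the sum of the largest diameters".

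The Study Summary, under Statistical Methodology, lists the same pair of correlations, including "and the correlation between change in ASL measured tumor perfusion and the corresponding tumor size change", with no restriction to progressors.

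On numbers, 10.2 says: "We expect approximately 50% of RCC patients to progress within 7 months of imaging protocol", and "we target 40 subjects for this study and anticipate approximately 20 subjects to progress within the 7 months period". It adds: "Beyond this time point, patients will be followed according to their clinical scans for the next 3 years or until death". Section 10.3 does not say whether a progressor is someone who progresses by 7 months or at any time in follow-up.

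Progression is judged by RECIST (10.1). Section 6.1.3.1 defines it as growth of at least 20% in the sum of longest diameters from the smallest recorded sum, or a new lesion. Section 6.1.3.2 adds unequivocal progression of non-target lesions.

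**The concern.** Restricting the time-to-progression correlation to progressors has an evident motive, since only they have an observed progression time. (Whether that deals properly with censoring is a separate matter.) The motive does not extend to perfusion change against size change, where a patient who never progresses contributes a complete pair of values.

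Two things are at stake. The first is precision: patients with usable data are dropped from an already small study, and 10.3 then repeats the analyses separately for men and women. The second is interpretation: the patients kept are chosen by a later outcome that depends partly on size, so the correlation among them need not equal the correlation among all treated patients. The two sections also give the analyst different analysis sets for the same analysis.

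**Working it through.** **Inputs.** 40 RCC patients, about 20 progressors by 7 months, r = 0.75, two-sided alpha 0.05 and power above 95% (all from 10.2). The value n = 30 is an assumption, standing for further progressors found in later follow-up. True correlations of 0.4 and 0.5 for perfusion against size are also assumptions, because the plan gives none.

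**Plan's own figure.** Fisher-z power is Φ(atanh(r)·√(n−3) − 1.960). With r = 0.75 and n = 20: 0.973 × 4.123 − 1.960 = 2.052, so power is 98%. The stated figure of more than 95% reproduces. It concerns time to progression only; no power is stated for perfusion against size.

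**Power for perfusion against size.** The same formula, with √17 = 4.123, √27 = 5.196 and √37 = 6.083:

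| True r | atanh(r) | n = 20 | n = 30 | n = 40 |
|---|---|---|---|---|
| 0.5 | 0.549 | 62% | 81% | 92% |
| 0.4 | 0.424 | 42% | 60% | 73% |

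For example, with r = 0.5 and n = 20: 0.549 × 4.123 − 1.960 = 0.305, and Φ(0.305) = 62%.

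**Detectable correlation.** For 80% power it is tanh((1.960 + 0.842)/√(n−3)): 0.59 at n = 20, 0.49 at n = 30 and 0.43 at n = 40.

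**Interval width.** At an observed r of 0 the 95% limits are ±tanh(1.960/√(n−3)): ±0.44 at n = 20 and ±0.31 at n = 40.

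**Selection, illustration only.** Let perfusion change P, size change S and a latent liability to progress L be jointly normal, and keep the upper half on L. The variance of L falls by the fraction k = 2/π = 0.637, and the correlation among progressors is

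(r_PS − k·r_PL·r_SL) / √[(1 − k·r_PL²)(1 − k·r_SL²)].

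All three correlations are assumed.

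- True r_PS = 0.5, r_SL = 0.7, r_PL = 0.75: (0.5 − 0.334)/√(0.642 × 0.688) = 0.25. The estimate is attenuated.
- True r_PS = 0.5, r_SL = 0.1, r_PL = 0.75: (0.5 − 0.048)/√(0.642 × 0.994) = 0.57. It is slightly inflated.
- True r_PS = 0, r_SL = 0.5, r_PL = 0.75: (0 − 0.239)/√(0.642 × 0.841) = −0.32. A correlation appears where there is none.

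Simulation over r_SL from 0.3 to 0.7 and r_PL from 0.5 to 0.75 gave 0.25 to 0.46 for a true 0.5 when half progress, and 0.34 to 0.47 when 75% progress. The distortion can go either way, and it shrinks as more patients progress.

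**The case against.** Several points against the concern are sound.

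- **The sample is not necessarily halved.** Twenty of 40 is the 7-month expectation, 10.3 sets no window, and follow-up runs for 3 more years. This stands, and is why n = 30 is shown. Power at n = 30 is still below that at n = 40.
- **Forty is a ceiling.** The Study Schema makes attendance at both early visits optional, and lesions of at least 20 mm are not an eligibility requirement, so some patients may lack a usable pair. This stands. It can also reduce the number of usable progressors.
- **Selection on size may be weak.** Section 5.4 does not expect size change before the clinical scans at 2 to 3 months, progression is measured from the smallest sum rather than from baseline, and new lesions and non-target progression also count. This stands against attaching a definite loss of power to selection.
- **The two correlations are to be compared.** They share the perfusion variable, so the comparison is simplest in the same patients. The plan does not offer this as its reason, but it is a good one for keeping a progressor-only version.
- **The analysis is secondary in standing.** It is not itself a listed objective and carries no power claim. This limits the weight of the point.

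A reader might also infer that the restriction pushes the result toward no correlation with size, and that this favours the trial's hypothesis. The documents do not support that. Losing patients widens the interval without shifting the estimate, and selection can move it either way. The hypothesis in 10.1 is that perfusion falls before size changes, not that the two are uncorrelated. The null finding cited in 10.2 concerns size change against time to progression, a different pair.

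**Conclusion.** The point holds in a limited form. Section 10.3 restricts the perfusion-size correlation to progressors without a stated reason, although the analysis needs no progression date, and the Study Summary states it unrestricted.

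If only the 20 expected 7-month progressors are used instead of 40 patients, power falls from 92% to 62% at r = 0.5 and from 73% to 42% at r = 0.4, and the correlation detectable with 80% power rises from 0.43 to 0.59. With 30 progressors the loss is smaller: 81% and 60%. These figures assume bivariate normal data, complete scans and the illustrative correlations named.

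The progressor-only estimate can also be distorted by selection, but its direction and size depend on correlations that the documents do not give. The conclusion is avoidable loss of information and an estimate that is harder to interpret. It is not a demonstrated bias in the trial's favour.

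**What to change.** In 10.3, take the perfusion-size correlation out of the clause that restricts the sentence to progressors. Make the main version an analysis of all RCC patients with an evaluable T0 scan and the corresponding follow-up scan, whatever their later progression status. Handle anti-angiogenic and immunotherapy patients as in objectives 2.1 and 2.3, where the former are primary and the latter exploratory, so that widening the set does not pool them by default.

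Keep the progressor-only version as a secondary analysis, so that the planned comparison with the time-to-progression correlation uses the same patients. State whether progressors are counted at 7 months or over all follow-up. Give the same populations in the Study Summary.

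The cost is a few sentences and one extra analysis, with no new data. The drawback is that the two main correlations will rest on different, overlapping samples, so they should be compared formally only in the common progressor set.
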